## 2.7.4 Other safety data

#### **2.7.4.1 Vital signs**

The summary of vital signs will only include treatment emergent data, which are defined as those vital sign measurements after the first dose of study treatment and up to last dose + 84 days.

Analysis in vital sign measurement using descriptive summary statistics for the change from baseline for each post-baseline visit will be performed. These descriptive summaries will be

presented by vital sign and treatment group. Change from baseline will only be summarized for participants with both baseline and post-baseline values and will be calculated as:

change from baseline = post-baseline value – baseline value

The number and percentage of participants with newly occurring notable vital signs will be presented. Criteria for notable vital sign abnormalities are provided in Table 2-6:

Table 2-6 Criteria for notable vital sign abnormalities

Vital sign (unit)	Notable abnormalities	
Systolic blood pressure (mmHg)	>= 140 mmHg or < 90 mmHg	
Diastolic blood pressure (mmHg)	>=90 mmHg or <60 mmHg	
Pulse (bpm)	> 100 bpm or <60 bpm	

#### 2.7.4.2 Compound specific safety evaluation

Safety topics of interest, such as risks defined in the RMP or topics of interest regarding signal detection or routine analysis are defined in the Program Case Retrieval Sheet that is stored in CREDI at the path Cabinets/CREDI Projects/A/AIN457A/Integrated Medical Safety.

The crude incidence and exposure-adjusted incidence rates for RMP risks will be summarized.

**Important note:** For the evaluation of RMP risks primary and secondary system organ classes of the MedDRA dictionary will be considered.

## 2.8 Pharmacokinetic endpoints

AIN457 serum concentration data will be listed by treatment, participant, and visit/sampling time point. Descriptive summary statistics will be provided by treatment and visit/sampling time point, including the frequency (n, %) of concentrations below the Lower Limit of Quantification (LLOQ) and reported as zero.

Concentrations below LLOQ will be imputed by 0 in summary statistics. No pharmacokinetic parameters will be calculated in this study as sparse sampling does not allow valid estimation by non-compartmental analysis.

## 2.9 PD and PK/PD analyses

#### 2.9.1 Immunogenicity

Each anti-drug anti-body (ADA) sample is assessed in a three-tiered ADA testing approach. All ADA samples are analyzed in the initial screening assay (first tier). Samples testing positive in the screening assay are then subjected to the confirmatory assay to demonstrate that ADA are specific for the therapeutic protein product (second tier). The titer of confirmatory positive samples will be subsequently determined in the titration assay (third tier).

Samples identified as positive in the confirmatory assay are considered ADA positive and are further characterized in the neutralization assay to indicate the presence of neutralizing antibodies (NAb).

Any ADA sample collected after 84 days of the last dose of AIN457 will not be used for summaries or derivations and will only be included in the listing.

The following summaries of ADA subject status (n and %) will be provided by visit using the safety set:

- Subjects with ADA-positive sample at baseline
- Subjects with ADA-positive NAb sample at baseline (if applicable)

A listing of ADA subject status will also be provided.

## 2.10 Patient-reported outcomes

Patient reported outcomes will be evaluated based on FAS.

#### **WORC Total**

The WORC is a patient reported outcome tool, uniquely developed for rotator cuff conditions by Kirkley and co-workers (Kirkley et al 2003). The WORC is self-administered and consists of 21 items divided into five domains: Physical Symptoms (6 items); Sport/Recreation (4 items); Work Function (4 items); Lifestyle Function (4 items) and Emotional Function (3 Items).

For ease of interpretation and in accordance with recommendations from instrument authors (Kirkley et al 2003), the WORC score will be calculated for the total score as well as the five domains.

The average of the non-missing items will be used to calculate the raw domain score where there are two or fewer missing items for the physical symptoms domain and one or fewer missing items for each of the sports/recreation, work, lifestyle, and emotions domains. Each domain raw score will be computed by summing the non-missing item scores, dividing by the number of non-missing items and multiplying by the total number of items in the scale. For the WORC total score to be derived, scores for all five domains need to be present. The algorithms for calculating the raw scores are as follows:

WORC Total raw score =  $21 \times (\text{sum of non-missing items/number of non-missing items})$ 

WORC Physical Symptoms raw score =  $6 \times \text{(sum of non-missing items/number of non-missing items)}$ 

WORC Sports/Recreation raw score =  $4 \times (\text{sum of non-missing items/number of non-missing items})$ 

WORC Work raw score =  $4 \times (\text{sum of non-missing items/number of non-missing items})$ 

WORC Lifestyle raw score =  $4 \times (\text{sum of non-missing items/number of non-missing items})$ 

WORC Emotions raw score =  $3 \times (\text{sum of non-missing items/number of non-missing items})$ 

For raw scores, higher scores indicate worse (more symptomatic) status.

Specifically, for each the raw aggregate score, the total is subtracted from the maximum score and divided by the number of items, resulting in a scale of 0 to 100, where 0 represents the most symptomatic score and 100 represents no symptoms:

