9.4.4 Patient reported outcomes

WORC Total

The average of the non-missing items will be used to calculate the raw domain score where there are two or fewer missing items for the physical symptoms domain and one or fewer missing items for each of the sports/recreation, work, lifestyle, and emotions domains. Each domain raw score will be computed by summing the non-missing item scores, dividing by the number of non-missing items and multiplying by the total number of items in the scale. For the WORC score to be derived, scores for all five domains need to be present. Specifically, for each the raw aggregate score, the total is subtracted from the maximum score and divided by the number of items, resulting in a scale of 0 to 100, where 0 represents the most symptomatic score and 100 represents no symptoms:

See Section 9.4.1 Efficacy and/or Pharmacodynamic endpoint(s) for details.

WORC Physical Symptom domain

In line with WORC Total analysis, the data are converted to a percent score by inverting the raw score and then converting to a score out of 100 (Kirkley et al 2003).

[figure not shown]
The following variables will be evaluated:

- WORC PSD score: see Section 9.3 Primary endpoint(s)/estimand(s) analysis for details.
- Response in WORC PSD: see Section 9.4.1Efficacy and/or Pharmacodynamic endpoint(s) for details.

PROMIS-SF Upper Extremity score

See Section 9.4.1Efficacy and/or Pharmacodynamic endpoint(s) for details.

9.6 (Other) Safety analyses

Not applicable

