## **WORC Physical Symptom domain**

The WORC PSD comprises 6 questions (with a maximum score of 60 possible) that capture the key symptoms experienced by participants with RCT relating to pain, weakness, stiffness, and mechanical symptoms. A score of 0 is the best outcome in terms of physical symptoms and a score of 60 is the worst possible score.

In line with WORC Total analysis, the data are converted to a percent score by inverting the raw score and then converting to a score out of 100 (Kirkley et al 2003).

WORC PSD will be collected by a separate questionnaire in the e-diary which is completed by the participant at home.

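### SAP 2.10 prorates missing WORC items by domain for the domain scores but by the grand mean for the total, so with uneven missing items the total need not equal the sum of its domains

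*SAP*

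**What the plan says.** SAP 2.10 (WORC Total) lists 21 items in five domains: "Physical Symptoms (6 items); Sport/Recreation (4 items); Work Function (4 items); Lifestyle Function (4 items) and Emotional Function (3 Items"). A domain can be scored with "two or fewer missing items for the physical symptoms domain and one or fewer missing items for each of the sports/recreation, work, lifestyle, and emotions" scales. The domain raw score comes from "summing the non-missing item scores, dividing by the number of non-missing items and multiplying by the total number of items in the scale". A total exists only if all five domain scores exist: "For the WORC total score to be derived, scores for all five domains need to be present".

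The SAP then gives one formula per score. For the total it is 21 × ("sum of non-missing items/number of non-missing items"), taken over the whole questionnaire. The domain scores thus decide whether a total exists but do not enter its value.

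Protocol 9.4.4 has the same domain rule ("Each domain raw score will be computed by summing the non-missing item scores, dividing by the number of non-missing items") and the same five-domain condition. Its readable text gives no separate raw-score formula for the total.

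The WORC total is used in three places: the secondary endpoint of a gain of at least 50 points at Week 16 (SAP 2.6.1), the baseline table (SAP 2.3.2), and inclusion criterion 5, a total of 40 or less at Screening and Baseline (Protocol 5.1).

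**The concern.** A total that requires all five domain scores would naturally be built from them. Summing the prorated domains keeps the domain weights at 6:4:4:4:3 whatever is missing. The grand mean lowers the weight of any domain with a missing item and raises the others. If a participant leaves out items in the domain that is worst for them, the total looks better than the domain scores reported beside it. The reverse happens if the items come from a mild domain.

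At stake are the agreement of the total with its own domains and, for a participant close to the 50-point gain, the responder classification.

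**Working it through.** **The plan's own figure.** The only stated figure tied to the total is the 97% power for WORC-TOT50 in SAP 3.2 (50% v 25%, 117 per group). With pooled variance under the null and two-sided 5%, the null SE is √(2 × 0.375 × 0.625/117) = 0.0633 and the alternative SE is √((0.25 + 0.1875)/117) = 0.0611. Then z = (0.25 − 1.96 × 0.0633)/0.0611 ≈ 2.06, so power is 98.0% (98.3% unpooled). That is close to the stated value. It rests on assumed response rates, so it does not test the scoring rule.

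**Inputs**
- Items per domain: 6, 4, 4, 4, 3 (SAP 2.10).
- Permitted missing items: up to 2, 1, 1, 1, 1 (SAP 2.10), giving 3 × 2 × 2 × 2 × 2 = 48 patterns.
- Item range 0 to 10, inferred from six PSD items "with a maximum score of 60 possible". The maximum total raw score is then 210, and the percent score is taken as 100 × (1 − raw/210).

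**Formulas**
- Domain sum: raw = Σ (items in domain × mean of that domain's answered items).
- SAP total: raw = 21 × (sum of all answered items / number answered).
- Difference on the percent scale, SAP minus domain sum: (100/210) × Σ (missing items in domain × [domain mean − grand mean]). It is zero when nothing is missing or when all domain means are equal.

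**Example profile.** Domain means are 6, 9, 8, 7, 5. The domain sum is 36 + 36 + 32 + 28 + 15 = 147, a score of 30.0 in every row.

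| Missing | Grand mean of answered items | SAP score | Gap |
|---|---|---|---|
| none | 147/21 = 7.00 | 30.0 | 0 |
| one sport item | 138/20 = 6.90 | 31.0 | +1.0 |
| one in each 4-item domain | 123/18 = 6.83 | 31.7 | +1.7 |
| two PSD items | 135/19 = 7.11 | 29.0 | −1.0 |

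In the second row the missing sport item counts as 9.0 in its domain score and as 6.9 in the total.

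**Responder status.** Baseline is complete with every item 8: raw 168, score 20. At Week 16 two PSD items are missing and the answered items are 2, 3, 4, 4, 2 by domain.
- Domain sum: 12 + 12 + 16 + 16 + 6 = 62, score 70.48, gain +50.48: responder.
- SAP formula: 21 × 58/19 = 64.11, score 69.47, gain +49.47: non-responder.

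**Upper bound.** Over the 48 patterns the largest possible gap is 9.5 points, with two PSD items and one emotions item missing. The weight of each 4-item domain rises by 4/18 − 4/21 = 0.0317, and 3 × 0.0317 = 0.095. With one item missing the bound is 3.6 to 4.3 points. These bounds need domains at opposite ends of the scale.

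**Frequency, under assumptions.** The documents give no item-missingness rate. An illustrative simulation took independent item missingness of 2% to 10%, a between-domain SD of 1 and an item SD of 1.2. The two versions of the change score then differ with an SD of 0.4 to 0.8 points, and responder status differs in about 0.4% to 1.1% of scorable participants.

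**The case against.** The SAP's rule is explicit, programmable and coherent: a completeness condition followed by whole-scale proration. Neither document says that the total is the sum of the domains, and the instrument paper cited for scoring is not available here. The WORC total is completed on site, and the coordinator checks for missing answers (Protocol 8.5.1.1). Endpoints are now descriptive, with 21 randomized at termination (SAP 1). At 0.4% to 1.1%, that is about 0.1 to 0.2 of a participant. All of this stands and limits the effect. It does not explain why one missing item should take two values in the same questionnaire, and SAP section 4 gives no reason for it.

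A reader might infer more than the documents support:
- **That the five-domain condition does nothing.** It decides whether a total exists. With two sport items missing there is no sport score and so no total.
- **That the total ignores the affected domain.** The grand mean includes that domain's remaining items.
- **That the 40-point endpoints move.** These are gains in PSD, a single domain, for which the two prorations coincide.
- **That eligibility is decided by the wrong formula.** The entry score is computed by the device, and its formula is not given. Answers of 5, 5, 7, 7, 6 by domain with two PSD items missing give 40.95 by domain sum and 40.00 by the SAP formula, so a mismatch could matter, but none is shown.
- **That protocol and SAP conflict.** The readable protocol text has no total formula to conflict with.

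**Conclusion.** The inconsistency is real and minor. SAP 2.10 uses two prorations, so the total can differ from the sum of its prorated domains when items are missing unevenly and domain means differ. In the example profile the gap is 1.0 to 1.7 points, enough to reverse WORC-TOT50 status only near the cut-off. The 9.5-point maximum is an arithmetic bound and should not be read as the expected effect. With complete questionnaires nothing changes, and the primary endpoint is untouched.

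The size rests on 0 to 10 items, the linear percent conversion and, for the frequency, assumed missingness. No test depends on it. With roughly 10 participants per arm, a single reclassification would move a reported response rate by about 10 percentage points (1/10), but even one is unlikely. This is an improvement at almost no cost and does not undermine the analysis.

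**What to change.** In SAP 2.10, replace the total formula with: WORC Total raw score = sum of the five prorated domain raw scores, derived only when all five are available. Check that the e-device total used for the entry criterion follows the same rule, and record the answer. If the sponsor does intend the grand mean, say so explicitly and note that the total may then differ from the sum of the domains. The cost is one line of SAP text, one line of code and one query to the device vendor. No new data are needed.

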## **WORC Physical Symptom domain**

The WORC PSD comprises 6 questions (with a maximum score of 60 possible) that capture the key symptoms experienced by participants with RCT relating to pain, weakness, stiffness, and mechanical symptoms. A score of 0 is the best outcome in terms of physical symptoms and a score of 60 is the worst possible score.

In line with WORC Total analysis, the data are converted to a percent score by inverting the raw score and then converting to a score out of 100 (Kirkley et al 2003).

WORC PSD will be collected by a separate questionnaire in the e-diary which is completed by the participant at home.

# Patient Reported Outcomes Measurement Information System (PROMIS)-Short Form (SF) Upper Extremity

PROMIS SF UE measures self-reported capability of Physical Function. Participants will complete this questionnaire on site and will be asked a series of 7 questions rating their ability to perform a range of physical activities related to daily life that would be impacted by shoulder function. Each response is scored from 5 (Without any difficulty) to 1 (Unable to do). The 7 scores are added to give a total score out of 35. The lowest possible raw score is 7; the highest possible raw score is 35. Total raw score will be translated into a T-score (see Appendix 5.6) for each participant. The T-score rescales the raw score into a standardized score with a mean of 50 and a standard deviation (SD) of 10. There is no recall period for this questionnaire.

#### 2.12 Other Exploratory analyses

Due to the premature study discontinuation, exploratory objectives and endpoints will not be analyzed.

## 3 Sample size calculation

## 3.1 Primary endpoint(s)

An overall type I error (2-sided) of 5% will be used to control type I error. Secukinumab 300 mg s.c. will be tested versus placebo with respect to the primary endpoint (change from BSL in the WORC PSD score at Week 16). A sample size of 117 participants per group is deemed appropriate to achieve adequate power for the primary and secondary endpoints for this study.

The mean changes from BSL in the WORC PSD score at Week 12 for secukinumab 300 mg s.c. and placebo are 45.3 (SD = 25.64) and 28.5 (SD = 28.81), respectively; while the mean changes from BSL in the WORC PSD score at Week 14 for secukinumab 300 mg s.c. and placebo are 47.9 (SD = 24.47) and 35.1 (SD = 27.78), respectively, in participants with moderate to severe RCT based on data from the POC study (safety set). With 117 participants per treatment group, there would be approximately 95% power to detect a treatment difference of 14 with a SD of 30 in the mean change from BSL in the WORC PSD score between secukinumab and placebo in the evaluation of the primary efficacy hypothesis at Week 16 (two sample z-test, nQuery 8.4). The overall sample size were planned to be 234 participants for a randomization ratio of 1:1.

## 3.2 Secondary endpoint(s)

The estimated power with the chosen sample size based on data from the POC study are summarized in Table 3-1 and Table 3-2.

Table 3-1 Summary of power for continuous secondary endpoints

Endpoint	Mean difference	SD	Power
PROMIS SF UE  at Week 16	1.2	3	84%
WORC PSD at Week 24	14	30	95%

 $^{1}$  Considering the missing data due to potential PROMIS SF UE translation issues in China , N = 110 per treatment group was used for the power calculation.

Table 3-2 Summary of power for binary secondary endpoints

Endpoint	Response Rate		Power
	Secukinumab (N=117)	Placebo (N=117)	
WORC-PSD40  at Week 16	60%	35%	97%
WORC-TOT50  at Week 16	50%	25%	97%
WORC-PSD40  at Week 24	60%	35%	97%

<sup>1 WORC-PSD40: Proportion of participants achieving an increase of at least 40 points from BSL in WORC PSD score

<sup>2 WORC-TOT50: Proportion of participants achieving an increase of at least 50 points from BSL in WORC total score

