9.4 Secondary endpoint(s)/estimand(s) analysis

9.4.1 Efficacy and/or pharmacodynamic endpoint(s)

Two studies of identical design (CAIN457012301 and CAIN457012302) are planned, each with multiple endpoints. The primary endpoint and secondary endpoints will be tested in each of the two studies separately. Secondary endpoints at Week 24 will be tested using participants who have reached Week 24 at the time of the Week 16 DBL. In order to control for the type I error rate ('false positive rate') at the level of the individual studies, the testing strategy illustrated in Figure 9-1 below will be implemented. The full alpha=0.05 will be spent at the Week 16 primary analysis.

The following null hypotheses will be included in the testing strategy:

Primary objective:

H₁: secukinumab 300 mg + SoC is not different to placebo + SoC with respect to change from BSL in the WORC PSD score at Week 16

Secondary objectives:

 H_2 : secukinumab 300 mg + SoC is not different to placebo + SoC with respect to proportion of participants achieving an increase of at least 40 points from BSL in the WORC PSD score at Week 16

H₃: secukinumab 300 mg + SoC is not different to placebo + SoC with respect to proportion of participants achieving an increase of at least 50 points from BSL in the WORC total score at Week 16

[figure not shown]
H₄: secukinumab 300 mg + SoC is not different to placebo + SoC with respect to change from BSL in the PROMIS-SF Upper Extremity score at Week 16

H₅: secukinumab 300 mg + SoC is not different to placebo + SoC with respect to proportion of participants achieving an increase of at least 40 points from BSL in the WORC PSD score at Week 24

H₆: secukinumab 300 mg + SoC is not different to placebo + SoC with respect to change from BSL in the WORC PSD score at Week 24

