9.8 Interim analysis

Interim analysis is not applicable in this study.

The primary endpoint analysis will be performed after all participants have completed the Week 16 visit or discontinued earlier. The primary endpoint analysis will be used for regulatory submission. The Investigator, site personnel, persons performing the assessments and participants will continue to remain blinded to the original treatment assignment that each participant received at randomization until after the DBL for Week 24 analysis. At the time of the Week 16 DBL, the Week 24 secondary endpoints will be evaluated in participants who have already reached Week 24. The full alpha=0.05 will be spent at the Week 16 DBL.

Subsequent to the primary endpoint analysis, the final CSR analysis is planned after participants have completed the Week 24 assessments and may be used for regulatory submission and/or publication purposes. Additional analyses may be performed to support interactions with health authorities, as necessary.

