9.9.2 Secondary endpoint(s)

The estimated power with the chosen sample size based on data from the POC study are summarized in Table 9-1 and Table 9-2.

Table 9-1 Summary of power for continuous secondary endpoints

Endpoint	Mean difference	SD	Power
PROMIS-SF Upper Extremity ¹ at Week 16	1.2	3	84%
WORC PSD at Week 24 ²	14	30	85%

¹ Considering the missing data due to potential PROMIS-SF Upper Extremity translation issues in China, N = 110 per treatment group was used for the power calculation.

Table 9-2 Summary of power for binary secondary endpoints

	Response Rate		
Endpoint	Secukinumab (N=117)	Placebo (N=117)	Power
WORC-PSD40 ¹ at Week 16	60%	35%	97%
WORC-TOT50 ² at Week 16	50%	25%	97%
WORC-PSD401 at Week 243	60%	35%	87%

¹WORC-PSD40: Proportion of participants achieving an increase of at least 40 points from BSL in WORC PSD score

² Assuming 70% participants will complete Week 24 or discontinue early at the Week 16 DBL, the sample size will be 164 (N = 82 per treatment group).

² WORC-TOT50: Proportion of participants achieving an increase of at least 50 points from BSL in WORC total score

³ Assuming 70% participants will complete Week 24 or discontinue early at Week 16 DBL, the sample size will be 164 (N = 82 per treatment group).

10 Supporting documentation and operational considerations

Page 92 of 107

Protocol No. CAIN457O12301

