#### 1 Introduction

The scope of this plan includes the primary and secondary analyses. The purpose of this amendment is to modify the analysis plan to reflect the early termination status of the study. At the time of termination, 21 patients had been randomized and 2 patients had completed the study. Patients who were screened by May 7, 2024 were permitted to continue in the study per protocol to study completion.

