## 2.6.2 Statistical hypothesis, model, and method of analysis

The secondary objectives will be analyzed in a purely descriptive manner. Categorical variables will be presented in frequency tables. PROMIS change from baseline over time will be presented by treatment group using a summary table. No testing strategy will be applied.

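### SAP Tables 3-1 and 3-2 state 95% and 97% power for the two Week 24 endpoints; the protocol's planned Week 24 test, at 82 per arm, has 85% and 87%.

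*SAP*

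**What the plan says.** SAP Section 3.2 tabulates power for the secondary endpoints. The Week 24 change-score row of Table 3-1 reads "WORC PSD at Week 24 14 30 95" (per cent). It carries no sample size of its own. Table 3-2 is headed N=117 in both arms and gives 97% for WORC-PSD40 at Week 24, with response rates of 60% and 35%. One row in Table 3-1 does have a reduced sample size: for PROMIS, "N = 110 per treatment group was used for the power calculation".

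The protocol treats Week 24 differently. Section 9.4.1 says: "Secondary endpoints at Week 24 will be tested using participants who have reached Week 24 at the time of the Week 16 DBL". Section 9.8 repeats the rule: "At the time of the Week 16 DBL, the Week 24 secondary endpoints will be evaluated in participants who have already reached Week 24". Protocol Tables 9-1 and 9-2 then carry a footnote to both Week 24 rows: "Assuming 70% participants will complete Week 24 or discontinue early at the Week 16 DBL, the sample size will be 164", that is, 82 per arm. On that basis they give 85% for the change score (difference 14, SD 30) and 87% for the response (60% and 35%).

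The current SAP was rewritten after the trial was stopped: "At the time of termination, 21 patients had been randomized and 2 patients had completed the study". For the secondary endpoints, Section 2.6.2 states "No testing strategy will be applied".

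**The concern.** The two documents give different power for the same two hypotheses (H5 and H6 in the protocol), with identical differences, SDs and response rates. The remaining secondary rows (PROMIS, WORC-PSD40 and WORC-TOT50 at Week 16) agree. Only the Week 24 rows differ, and those are the rows that carry a footnote in the protocol and none in the SAP.

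Nothing in the SAP accounts for the difference. The May 2024 entry in its document history lists parts of Sections 1 and 2 but not Section 3. The November 2024 entry names no section. Section 4 attributes changed analyses to early termination, which cannot alter what power was planned.

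At stake is the accuracy of the design record. A reader of the SAP alone would think the last two steps of the testing sequence had been planned with power 10 percentage points higher than the protocol states.

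**Working it through.** **Inputs**

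- Type I error, SAP 3.1: "An overall type I error (2-sided) of 5% will be used to control type I error", so the critical value is 1.96.
- Method for the continuous endpoint: two-sample z-test, named for the primary endpoint in Protocol 9.9.1 and SAP 3.1. It is assumed here for Week 24 as well.
- Change score: difference 14, SD 30 (both documents).
- Response: 60% v 35% (both documents).
- Sample size per arm: 117 (SAP 3.1 and the Table 3-2 heading), or 82 (Protocol 9.9.2; 0.70 × 234 = 163.8, rounded to 164, or 82 per arm).

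**Change in WORC PSD at Week 24**

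Power = Φ(14 / (30·√(2/n)) − 1.96)

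- n = 117 (the SAP's figure first): 14/3.922 = 3.569; 3.569 − 1.96 = 1.609; Φ = 0.946. This matches the stated 95%.
- n = 82: 14/4.685 = 2.988; 2.988 − 1.96 = 1.028; Φ = 0.848. This matches the protocol's 85%.

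The smallest n that rounds to 95% is 117 (n = 116 gives 0.9445). So although Table 3-1 prints no N for this row, the 95% is a 117-per-arm figure. A t-test changes little: 94.5% and 84.4%.

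**WORC-PSD40 at Week 24**

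Power = Φ((0.25 − c − 1.96·SE₀) / SE₁), where

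- SE₀ = √(2 × 0.475 × 0.525 / n)
- SE₁ = √((0.60 × 0.40 + 0.35 × 0.65) / n)
- c = 0 without a continuity correction, or 1/n with it.

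| n per arm | SE₀ | SE₁ | Uncorrected | Corrected | Stated |
|---|---|---|---|---|---|
| 117 | 0.0653 | 0.0632 | 97.3% | 96.4% | 97% (SAP) |
| 82 | 0.0780 | 0.0755 | 90.1% | 87.0% | 87% (protocol) |

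Exact enumeration of the chi-square test at n = 82 gives 90.1% uncorrected and 87.1% corrected. With an unpooled variance it is 91.2%. No two-sided variant at 82 per arm comes within 2 points of 95% for the change score or 97% for the response; the highest values are 84.8% and 91.2%.

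**Comparison with the PROMIS row**

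Power = Φ(1.2 / (3·√(2/n)) − 1.96) gives 84.3% at n = 110 and 86.4% at n = 117. The stated 84% therefore uses the reduced N. The same SAP table adjusts for a loss of 7 per arm in PROMIS but not for a loss of 35 per arm at Week 24.

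**The case against.** The strongest reply is that the SAP's arithmetic is correct for the N it uses. Section 3.2 describes power at the chosen sample size, Section 3.1 sets that at 117 per group, and the SAP's own list of Week 24 endpoints (Table 1-1 and Section 2.6.1) does not carry the restriction to data available at the Week 16 lock. On that reading the tables describe a full Week 24 evaluation, and without the March 2023 SAP one cannot tell a copying slip from an undeclared choice. It is true that the calculation is right for 117 and that the origin of the discrepancy is unknown. But Section 3 describes the trial as planned, and the planned Week 24 test was the restricted one. A move to full Week 24 data would depart from Protocol 9.4.1 and 9.8 and would need declaring in Section 4.

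Three narrower points stand in part:

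- The 82 per arm comes from the protocol's 70% assumption, not from the testing rule alone. Purely as illustration, 60% availability (n = 70) would give 78.8% and 80.5% (corrected), and 90% (n = 105) would give 92.2% and 94.3%. Even at 90%, both remain below the SAP's figures.
- The protocol's 87% needs a continuity correction that neither document mentions, and no single method tried matches every row of Protocol Table 9-2 to the nearest per cent. With the correction, WORC-PSD40 at 117 is 96.4% against a stated 97%. Without it, WORC-TOT50 at 117 is 98.0% against 97%. Uncorrected, the Week 24 response still has 90.1%, about 7 points short of 97%.
- The planned tests were a repeated-measures model and a covariate-adjusted logistic regression, so every figure here is an approximation from an unadjusted comparison. That applies equally to both documents and does not explain the gap between them.

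**Conclusion.** The concern holds. The SAP's 95% and 97% are figures for 117 per arm, whereas the planned Week 24 test at the protocol's assumed 82 per arm has 85% and 87%. The overstatement against the protocol is 10 percentage points in each row. By recalculation it is 94.6% against 84.8% for the change score, and 97.3% against 90.1% (uncorrected) or 96.4% against 87.0% (corrected) for the response. These values rest on the 70% availability assumption and on unadjusted two-sample approximations; the protocol's 87% also rests on the continuity correction.

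The importance is low. Superiority testing has been dropped and the analyses are descriptive, so no estimate, test or conclusion changes. What is wrong is the SAP's account of the original design.

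**What to change.** In SAP Section 3.2, change the Week 24 cells to 85% (Table 3-1) and 87% (Table 3-2), and add to each row the footnote from Protocol 9.9.2: 70% of participants assumed to have completed Week 24 or discontinued by the Week 16 lock, 164 in total, 82 per arm. A short note that the 87% includes a continuity correction would make it reproducible, if the sponsor confirms that one was used.

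If the sponsor did intend complete Week 24 data, the alternative is to keep 95% and 97%, label both rows as assuming 117 per arm with full Week 24 data, and record the departure from the protocol in Section 4.

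The cost is SAP wording only: two cells and one footnote per table. No data, analysis or output is affected. The stated power becomes less favourable.
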